833 A test of superiority will be used in evaluating the following hypotheses for the primary outcome:

834 Null Hypothesis (H_0): There is no difference in the mean change in CST from baseline to 4 months
835 between photobiomodulation (PBM) and sham groups.

836 Alternative Hypothesis (H_a): There is a difference in the mean change in CST from baseline to 4
837 months between PBM and sham groups.

838 Similar hypothesis tests will be conducted for all secondary, exploratory, and safety outcomes.

839 **7.3 Sample Size**

840 **7.3.1 Outcome Projections:**

841 To estimate the standard deviation (SD) of change in OCT CST, data from the DRCR Retina
842 Network Protocol A (Treatment for Central-Involved Diabetic Macular Edema in Eyes with Very
843 Good Visual Acuity) was used. The Protocol A cohort of eyes with 20/25 baseline visual acuity
844 and central subfield thickening treated with modified-ETDRS laser was used for the estimation.
845 In protocol A, 42 eyes in the modified-ETDRS laser group completed a visit within 4 months of
846 randomization. The SD of change in CST adjusted for baseline CST in these eyes was 50 microns
847 (personal communication, [name]). The mean change in CST was -2 microns.

848 The expected change and standard deviation of CST in an untreated group is unknown at this time.

849 **7.3.2 Sample Size Estimates**

850 Table 1 shows total sample size estimates under several scenarios. These calculations assume a
851 Type I error rate of 5%, 90% power, and a two-sided test of superiority (see Section 7.6) with a
852 null hypothesis of no difference between the groups (see Section 7.2).

853

854 **Table 1: Total Sample Size Under Various Assumptions for True Mean Change and**
 855 **Standard Deviation**

Mean Treatment Group Difference, microns	Change in Central Subfield Standard Deviation, microns (adjusted for baseline)			
	40	50	60	70
20	172	266	382	518
30	78	120	172	232
40	46	68	98	132

856 Assuming an effective standard deviation of 50 microns and a true difference in mean CST of 30
 857 microns, the required total sample size is 120 eyes to achieve 90% power. Sample size will be
 858 increased to 134 eyes to account for 10% lost to follow-up.

859 **7.4 Outcome Measures Phase 1 (Baseline to completion of the 4-Month/Primary outcome**
 860 **visit)**

861 *Primary Efficacy Endpoint(s)*: Mean change in CST from baseline

862 *Secondary Efficacy Endpoint(s)*:

- 863 • Mean change in retinal volume from baseline

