19 Study eyes will be assigned randomly to the two treatment groups in a 1:1 ratio stratified by site
20 and recent (within 4 months) or planned intravitreous treatment in the non-study eye, including
21 intravitreous anti-VEGF and steroid. Participants may have only one study eye enrolled in the
22 randomized trial.

23 **2.0 Efficacy Analysis Plan**

24 **2.1 Primary Outcome Analysis**

25 The primary analysis will consist of a treatment group comparison of mean change in CST from
26 baseline to the primary outcome visit using analysis of covariance, with adjustment for baseline
27 CST and the randomization stratification factor of recent or planned intravitreous treatment in
28 the non-study eye. Given that OCTs can be obtained from either Spectralis or Cirrus images, and
29 that values from these machines cannot be used interchangeably, OCT values will be converted
30 to a common value for reporting and analyses.

31 The primary analysis is an intention-to-treat analysis. All randomized eyes will be included in
32 the primary analysis irrespective of treatment received and will be analyzed according to
33 treatment group assignment at randomization.

34 For the primary analysis, study participants who complete the primary outcome visit without
35 missing data at the primary outcome visit will be considered as the **completer cohort**. Markov
36 chain Monte Carlo (MCMC) multiple imputation with 100 imputations will be used to handle
37 missing data for participants who do not complete the primary outcome visit, i.e., **non-**
38 **completer cohort**. The imputation model will be stratified by treatment group and will include

39 the CST measured at baseline and at all monthly interim visits up to the primary outcome visit
40 along with the randomization stratification factor of recent or planned intravitreous treatment in
41 the non-study eye.

42 For eyes that receive alternative treatment for DME (detailed in Protocol Section 3.6) in Phase 1,
43 data measured after the initiation of the alternative treatment will be considered to be missing
44 before entering the multiple imputation (MI) process, regardless of whether the treatment
45 initiation is per-protocol, and whether the participant completes the primary outcome visit. Then
46 after multiple imputation, the last OCT measurement prior to the initial alternative treatment
47 (LOCF data) will overwrite the MCMC imputed values for all post-treatment visits and will be

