76 function of observed baseline and follow-up characteristics included in the imputation model

77 (baseline CST, follow-up CST, treatment group, recent or planned intravitreous treatment in the
78 non-study eye), but not a function of the unobserved follow-up CST measurements that are being
79 imputed. This assumption cannot be tested since these data are unknown. However, a tipping
80 point analysis will be conducted which will adjust the imputed values for eyes without an
81 alternative DME treatment using a shift parameter and thereby determine how severe the
82 departure from MAR must be in order to change outcome of the primary analysis with respect to
83 rejecting or failing to reject the null hypothesis. A shift parameter will be applied to the imputed
84 values in the PBM group to determine the tipping point at which the results of the primary
85 analysis are nullified. That is, if one group is found to be superior ($P \leq .05$), the tipping point will
86 identify the shift parameter necessary to yield $P > .05$. Conversely, if the null hypothesis is not
87 rejected ($P > .05$), two tipping points will be identified – one that would make PBM superior and
88 one that would make sham superior. In either case, this tipping point(s) will be evaluated to
89 determine if it is plausible. If not, the MAR assumption is reasonable. For example, if the tipping
90 point were 500 microns, this would be evidence that the MAR assumption is reasonable for this
91 analysis.

92 The assumptions of linearity, normality, and homoscedasticity will be verified using graphical
93 methods. Serious violations may be addressed by transformation of dependent and/or
94 independent variables, non-parametric transformation, categorizing continuous covariates, and/or
95 excluding covariates. Transformation of the dependent variable (mean change in CST from
96 baseline) will be used to obtain valid P values while ensuring statistical model assumptions are
97 met. However, mean treatment group differences, rather than results based on transformed
98 outcomes will be reported for clinical interpretation.

99 A plot showing the mean converted level of CST values on OCT by treatment group over time
100 will be constructed using completers' data as defined above. In general, summary statistics (e.g.,
101 within-group means and standard deviations), will be based on completers' data while numbers

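### The tipping-point analysis shifts only the PBM arm, so it can overstate robustness when sham has more imputed eyes or the arms depart from MAR in opposite directions, and its result is misread as support for MAR

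*SAP*

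**What the plan says.** SAP 2.1 handles missing primary-outcome data by MAR imputation, stratified by treatment group: Markov "chain Monte Carlo (MCMC) multiple imputation with 100 imputations will be used to handle" them. Eyes given alternative DME treatment are carried forward instead and are not shifted.

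The SAP acknowledges that MAR cannot be tested and adds a tipping-point analysis. It first speaks of a shift parameter without naming an arm, then specifies that the shift goes to the imputed "values in the PBM group to determine the tipping point at which the results of the primary" analysis no longer hold. If the primary test is not significant, two tipping points are sought, one in each direction, with the same PBM shift.

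The tipping point is then examined to "determine if it is plausible. If not, the MAR assumption is reasonable. For example, if the tipping" point were 500 microns, the SAP would count that as support for MAR.

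No shift of the sham arm and no two-arm grid appears in SAP 2.1, in SAP Table 1 (sensitivity analyses #1 to #5) or in Protocol 7.6 and 7.7. The Table 1 analyses vary the use of complete cases, imputation, truncation and normal scores. None imposes a missing-not-at-random departure.

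**The concern.** There are two separate weaknesses.

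- **Coverage.** Eyes are imputed in both arms, and either arm's missing values may differ systematically from what MAR predicts. A PBM-only shift cannot show how the conclusion responds to a departure among sham eyes, or to departures in both arms at once. If few PBM eyes are imputed, the PBM shift has little leverage and the tipping point becomes large for that reason alone.
- **Inference.** A tipping point measures how far the data must depart from MAR before the conclusion changes. It carries no information on whether MAR holds. A large value caused by a small number of imputed PBM eyes would, under the stated rule, be read as support for the assumption.

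This is the only planned analysis that departs from MAR for the primary outcome, so what it leaves out is not picked up elsewhere.

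**Working it through.** **Inputs.** Protocol 7.3.2 sets a two-sided 5% test with 90% power: "Assuming an effective standard deviation of 50 microns and a true difference in mean CST of 30" microns, 120 eyes, "increased to 134 eyes to account for 10% lost to follow-up". Allocation is 1:1 (SAP 1.0), so 67 per arm.

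**The plan's own figure.** The normal approximation gives 2 x (1.960 + 1.282)^2 x 50^2 / 30^2 = 58.4, so 59 per arm or 118 in total. The noncentral-t calculation gives 120, as stated. 120 / 0.90 = 133.3, rounded up to 134. The plan's figures reproduce.

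**Assumptions.** 134 - 120 = 14 imputed eyes; several splits by arm; observed benefits of 25 and 30 microns; no covariates and no information from interim visits.

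**Formula.** Let m_P and m_S be the imputed eyes in PBM and sham, and D the observed benefit.

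- SE = 50 x sqrt(1/(67 - m_P) + 1/(67 - m_S)), from observed eyes only.
- Slack = D - 1.96 x SE.
- PBM-only tipping shift = slack x 67 / m_P (missing PBM eyes thicker than imputed).
- Sham-only tipping shift = slack x 67 / m_S (missing sham eyes thinner than imputed).
- Equal and opposite shifts in both arms = slack x 67 / (m_P + m_S) each.

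**Worked case, D = 25, 4 PBM and 10 sham.** SE = 50 x sqrt(1/63 + 1/57) = 9.14. Slack = 25 - 17.9 = 7.1. PBM only: 7.1 x 67/4 = 119. Sham only: 7.1 x 67/10 = 47. Both: 7.1 x 67/14 = 34.

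**Cross-check.** The closed form holds the SE fixed, but shifting a subset of eyes also widens the spread within that arm. Constructed datasets with 100 imputations combined by Rubin's rules, without truncation, therefore tip somewhat earlier. The ranges below run from that calculation to the closed form (microns).

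| Benefit | Imputed PBM/sham | PBM only | Sham only | Opposite, each arm |
|---|---|---|---|---|
| 25 | 7/7 | 60-68 | 58-68 | 32-34 |
| 25 | 4/10 | 100-119 | 42-47 | 32-34 |
| 25 | 2/12 | 176-236 | 36-39 | 30-34 |
| 30 | 7/7 | 98-116 | 98-116 | 52-58 |
| 30 | 4/10 | 160-202 | 72-81 | 52-58 |
| 30 | 2/12 | 280-404 | 60-67 | 52-58 |

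If the split is reversed (10 PBM, 4 sham, benefit 25), the closed form gives 47 for PBM only and 119 for sham only.

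The same arithmetic applies to a non-significant result. With an observed benefit of 10 microns and a 4/10 split, 17.9 - 10 = 7.9 microns are needed to make PBM superior. That is 7.9 x 67/4 = 133 for PBM only and 7.9 x 67/10 = 53 for sham only.

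**Two checks on the size.** Taking the SE from all 67 eyes per arm (8.64) would count imputed eyes as fully observed and inflate the result: (25 - 16.9) x 67/7 = 77 instead of 68 at 7/7. The SAP does not say whether truncation at 3 SD comes before or after the shift. Truncating last changes little at benefit 25 with 4/10 (102 for PBM only, 44 for sham only, 32 for both).

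**The case against.** The case for leaving the plan alone has real force.

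- **The sham-only problem is conditional.** At 7/7 a sham-only shift adds nothing. If PBM loses more eyes, the planned shift is the more sensitive test. If 14 missing eyes fell at random, 10 or more would be in sham with probability about 8%.
- **At the design effect the departure is not small.** With a 30-micron benefit and sham-heavy loss, the sham-only value is 60-81 microns, or 1.2-1.6 SD.
- **Direction.** To remove a PBM benefit, missing sham eyes must be thinner than imputed. Sham eyes that worsen and receive alternative treatment are carried forward and never shifted. Shifting the active arm tests the more obvious threat to a claimed benefit.
- **Partial cover.** The SAP frames the aim as finding how severe a departure must be, and visit completion is tabulated by arm, so a reader could see when few PBM eyes carry the shift.

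All of this stands, and it limits the point. It does not answer the case of opposite departures, which roughly halves the tipping point even with equal missingness, or the step from a large tipping point to MAR.

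A reader might infer from the different light in the two devices that sham will lose more eyes. The documents do not support that. They give one overall 10% loss. Participants are masked, the devices are described as otherwise identical, and sham participants may receive the active device after the 4-month visit. SAP 4.0 allows that controls may be less compliant, but that concerns device use, not dropout.

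**Conclusion.** The point holds in a limited form. The PBM-only shift can overstate robustness when more sham than PBM eyes are imputed, or when the arms depart from MAR in opposite directions. For a significant benefit near 25 microns and a 4/10 split, the planned figure would be at least 2 SD (100-119 microns), while a sham departure under 1 SD (42-47 microns) removes significance. With 7/7 the planned figure is 60-68 microns, against 32-34 in each arm for opposite shifts. These sizes rest on the assumed splits, SD 50, 14 imputed eyes and imputation without interim visits.

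The reading of an implausible tipping point as support for MAR is unsound whatever the split.

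A reader might go further and conclude that the primary result is unreliable, or that the planned test is always the weaker one. Neither follows. SAP 8.6 bases the primary conclusion on the primary analysis alone, so its P value is untouched, and with PBM-heavy loss the planned test is the stricter one.

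**What to change.** In SAP 2.1:

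1. Apply the shift to each arm independently over a two-way grid, and report the boundary where P crosses .05.
2. Report the number of imputed eyes per arm beside that boundary.
3. Replace the conclusion that MAR is reasonable with a statement on whether the primary conclusion is robust to plausible departures from MAR in either or both arms.

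The cost is one more loop over the existing imputations, a slightly larger table or plot, and a sentence of rewording. No new data are needed and the primary analysis does not change. This is a cheap improvement with slightly more output.

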48 used for the primary analysis. It is recognized that LOCF does not reflect the uncertainty in
49 outcomes (i.e., underestimates the variances) and is likely to introduce bias (of unknown
50 magnitude) into the primary analysis that favors the PBM group under the alternative hypothesis,
51 as participants may receive alternative treatment for falsely low visual acuity values, and some
52 eyes meeting criteria for and receiving alternative treatment might have recovered if they'd been
53 left untreated. However, the bias is not being increased by the MI since LOCF is applied after
54 MI. Also, in a recent study for a similar cohort, only 2 (<1%) out of 236 eyes in the observation
55 group initiated treatment without meeting pre-specified criteria during 2 years of follow-up,
56 therefore we expect very few eyes (if any) in this study will receive alternative DME treatment
57 against protocol.

58 To limit the influence of extreme data points, change in CST will be truncated at ± 3 SD after
59 imputation and LOCF to improve robustness of the treatment comparison. The cutoff values for
60 data truncation will be calculated using the primary outcome visit data within the completer
61 cohort, combining treatment groups, i.e. the “**completers’ data**”, which will consist of the
62 observed data for completers without alternative DME treatment, and the LOCF data for
63 completers who receive an alternative DME treatment.

64 Therefore, the **primary analysis dataset** will include:

65 • Data from completers without alternative DME treatment,
66 • MCMC imputed data for non-completers without alternative DME treatment,
67 • LOCF data for participants who receive an alternative DME treatment.

68 The *P* value, adjusted treatment group difference, and associated 95% confidence interval will be
69 reported for the treatment group effect with robust variance estimation using the primary analysis
70 dataset. If the *P* value for the test of the treatment effect is less than or equal to .05, then it will
71 be concluded that there is a significant difference for change in CST at the primary outcome
72 visits between the groups. In other words, if $P \leq .05$, the null hypothesis of no treatment effect
73 will be rejected.

74 Multiple imputation assumes that data are missing at random (MAR). In the present study, this
75 would mean that whether follow-up CST measurements are missing or observed may be a

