102 from statistical models (e.g., treatment group differences, confidence intervals, and P values)
103 will be based on primary analysis data as noted above.

104 **2.1.1 Sensitivity Analyses**

105 Sensitivity analyses for the primary outcome are listed in Table 1. In general, if the sensitivity
106 analysis results differ substantially from the primary analysis results, exploratory analyses will
107 be performed to evaluate factors that may have contributed to the differences.

108

109 **Table 1. Pre-Planned Sensitivity Analyses for the Primary Outcome of Mean Change in**
 110 **CST From Baseline at 4 Months**

| Eyes that receive an alternative DME treatment | Eyes that have missing data at primary outcome visit | Additional details | Rationale |
|--|---|---|---|
| Primary Analysis (MI, LOCF, then data truncation) | | | |
| 
 OCT data after alternative DME treatment will be considered missing for purposes of MI, hence will be imputed in the MI procedure Last OCT measurement prior to alternative DME treatment will then overwrite MI values and will be used for analysis (LOCF). | 
 MCMC multiple imputation for eyes with missing primary outcome data (MI) LOCF values will replace the imputed values for eyes that receive alternative DME treatment | Data truncation: changes in OCT from baseline will be truncated at ± 3 SD after multiple imputation based on cutoff values calculated from completers' data | There is no ideal way to handle eyes receiving alternative DME treatment in analysis. For the primary analysis, LOCF will be used for these eyes. It is recognized that LOCF will tend to bias results towards a larger treatment effect, assuming a treatment effect exists. Sensitivity analyses will be performed to evaluate possible impact of LOCF on study conclusions (#2, #4, #5 below). |
| Sensitivity Analysis #1 (Complete-case analysis with LOCF) | | | |
| LOCF for eyes receiving alternative DME treatment | Complete-case analysis, i.e., only eyes completing primary outcome visit will be included | Same rule for data truncation with primary analysis | To compare primary results including imputed data to results using observed data only. |
| Sensitivity Analysis #2 (MI for ALL eyes missing 4-month visit) | | | |

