414 of missing data and LOCF where applicable (i.e., raw data will be used for imputation).

415 **8.5 Model Assumptions**

416 All model assumptions, including linearity, normality of residuals, and heteroscedasticity, will be
417 verified. If model assumptions are not reasonably satisfied, then covariates may be categorized
418 or excluded, and a nonparametric approach, robust estimation method, or transformation may be
419 considered.

420 **8.6 Type I Error Rate**

421 There is no formal adjustment for multiplicity to compensate for the number of outcomes being
422 compared. All comparisons are conducted at alpha level 0.05 unless otherwise noted. In
423 particular, a number of sensitivity analyses and a non-ITT analysis are proposed along with the
424 primary analysis. The intent of these analyses is to explore the effect of primary analysis
425 assumptions on study conclusions, and if they are different, explain why. These analyses are not
426 a substitute for the primary analysis, and primary conclusion will be based on the pre-specified
427 primary analysis. Only 3 of the secondary outcomes of “primary interest” will be compared

428 statistically. Two of these, change in central subfield volume and percentage of participants
429 below the threshold for DME on OCT, are expected to be correlated with the primary outcome,
430 and are intended to help support and interpret the primary outcome findings and interpretation,
431 not to form the basis for independent conclusions.

432

433 **References**

434 Baker CW, Glassman AR, Beaulieu WT, et al. Effect of Initial Management With Aflibercept vs
435 Laser Photocoagulation vs Observation on Vision Loss Among Patients With Diabetic Macular
436 Edema Involving the Center of the Macula and Good Visual Acuity: A Randomized Clinical
437 Trial. *JAMA*. Published online April 29, 2019. doi:10.1001/jama.2019.5790

438 Benjamini Y, Hochberg Y. Controlling the False Discovery Rate: A Practical and Powerful
439 Approach to Multiple Testing. *Journal of the Royal Statistical Society Series B*
(Methodological). 1995;57(1):289-300.

441 Localio AR, Margolis DJ, Berlin JA. Relative risks and confidence intervals were easily
442 computed indirectly from multivariable logistic regression. *J Clin Epidemiol*. 2007;60(9):874-
443 882.

444 Sullivan TR, White IR, Salter AB, Ryan P, Lee KJ. Should multiple imputation be the method of

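### An implausibly large tipping point shows that the conclusion is robust, not that MAR is reasonable; the order of shift and truncation, and the report when no tipping point exists, are also unspecified

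*SAP*

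**What the plan says.** SAP 2.1 says of MAR: "This assumption cannot be tested since these data are unknown". It then introduces a shift parameter, applied to imputed values in PBM eyes without alternative DME treatment, to find how severe the "departure from MAR must be in order to change outcome of the primary analysis with respect to" rejecting or not rejecting the null hypothesis. After a significant result, one nullifying shift is sought. After a non-significant result, "two tipping points will be identified", one favouring each arm.

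The tipping point is then judged: the reader is to "determine if it is plausible. If not, the MAR assumption is reasonable". The worked example is that if the tipping "point were 500 microns, this would be evidence that the MAR assumption is reasonable for this" analysis.

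Truncation is described separately. In SAP 2.1 the cutoffs for "data truncation will be calculated using the primary outcome visit data within the completer" cohort, and truncation follows imputation and LOCF. SAP Table 1 heads the primary analysis "Primary Analysis (MI, LOCF, then data truncation". SAP 8.4 repeats that truncation comes after imputation "of missing data and LOCF where applicable (i.e., raw data will be used for imputation"). None of these places mentions the shift. The tipping-point analysis is not a row of Table 1, which settles truncation for the primary analysis and for each of the five numbered sensitivity analyses. The SAP gives no range of shifts to try and no instruction for when no tipping point is found.

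**The concern.** There are three linked faults.

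- **Inference.** The paragraph begins by saying MAR cannot be tested and ends with a rule for concluding that it is reasonable. A tipping point is computed from the observed data, the values imputed under MAR and a chosen shift. It takes the same value whether MAR is true or false, so it cannot be evidence for MAR.
- **Order of steps.** If truncation comes after the shift, large shifts are largely clipped away. If it comes before, they are not. Two programmers could report different tipping points from the same data.
- **Not reached.** The plan assumes that the tipping points always exist. They need not.

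This is the only planned analysis that deliberately departs from MAR for eyes missing the primary visit. In Table 1, analyses 1, 4 and 5 are complete-case, and 2 and 3 use imputation under MAR. As worded, the trial report could claim support for MAR when the result mainly reflects a small number of missing eyes.

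**Working it through.** **Inputs.** Protocol 7.3.2 gives a baseline-adjusted SD of 50 microns, a difference of 30, two-sided 5% and 90% power. The two-sample t calculation gives 59.35, so 60 per arm and 120 in total; 120/0.9 = 133.3, so 134. Both figures reproduce the protocol. With 1:1 allocation that is 67 per arm, and 10% loss is about 7 eyes per arm. The numbers of imputed eyes used below (m = 3, 5, 7, 10) are assumptions.

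**1. What drives the tipping point.** Shift m of 67 PBM eyes by s and allow for the variance that the shift adds. A result of −30 stops being significant when

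30 − m·s/67 = t × √[2·50²/67 + s²·(m/67)(1 − m/67)/67], with t = 1.978 (132 df).

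For m = 7 and s = 107, the left side is 30 − 11.2 = 18.8. The right side is 1.978 × √(74.6 + 16.0) = 1.978 × 9.52 = 18.8. Solving for each m gives 78, 107, 143 and 218 microns for 10, 7, 5 and 3 imputed PBM eyes. The missingness mechanism appears nowhere in the equation.

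**2. Simulation with MAR true in every trial.** The model was ANCOVA on treatment, baseline and stratum with robust variance. There were 100 imputations by arm, Rubin's rules, cutoffs at the completers' mean ±3 SD, equal numbers missing per arm, and shifts up to 3000 microns. Two runs were made, with raw SD of change 50 (400 trials per setting) and 58 (200 trials per setting).

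Significant results, true difference −30:

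| Imputed PBM eyes | Median tipping point, shifted values not truncated (microns) | No nullifying point, truncation last (run 1; run 2) |
|---|---|---|
| 10 | 80–90 | 9/355; 1/178 |
| 7 | 110–120 | 67/352; 10/174 |
| 5 | 150–160 | 147/363; 45/179 |
| 3 | 230–240 | 268/364; 115/187 |

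With the shift applied after truncation, a nullifying point existed in every one of these trials.

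Null results, at least one of the two points not reachable:

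| Imputed PBM eyes | Truncation last | Shift after truncation |
|---|---|---|
| 10 | 375/388; 153/193 | 0; 0 |
| 7 | 383/383; 195/195 | 0/383; 0/195 |
| 5 | 375/375; 192/192 | 0/375; 1/192 |
| 3 | 380/380; 186/186 | 380/380; 186/186 |

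After a null result with 5 imputed PBM eyes and no truncation of shifted values, the larger of the two tipping points had median 825–875 microns. That exceeds the SAP's 500-micron example in trials where the result says nothing about MAR.

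**3. Why truncation last removes a point.** With 7 imputed eyes centred near the completers' mean, truncation lets each move about 3 × 50 = 150 microns on average. The arm difference can then move about 7/67 × 150 = 15.7 microns. The standard error is at least 50 × √(2/67) = 8.64, so significance needs at least 1.978 × 8.64 = 17.1. After a null result, the farther of the two thresholds is always at least 17.1 away, so it cannot be reached.

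A simpler calculation without covariates or between-imputation variance shows the same:

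- Difference 0, m = 7, truncation last: a +500 shift gives a difference of 16.0 (P = .12), and no tipping point exists in either direction. Without truncation of shifted values, the points are ±235, and +500 gives 52.2 (P = .013).
- Difference −10, m = 7: the downward point is −80 either way. The upward point is absent with truncation last and +470 without truncation.

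**4. Why reordering does not cure every case.** The shift inflates the variance as well as the mean. As s grows, the test statistic tends to √[67m/(67 − m)]. At m = 3 this is √(201/64) = 1.77, below 1.96, so an arbitrarily large shift still does not give significance.

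**The case against.** The strongest reply is that this is loose wording in a paragraph that otherwise has the method right. The purpose is stated correctly, MAR is called untestable, and the example limits itself to this analysis, which could mean only that relying on MAR is acceptable for this test. That lowers the weight of the point but does not remove it: the rule and the example still treat a large shift as evidence for the assumption.

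Second, the SAP does not say that shifted values are truncated, and its 500-micron example makes sense only if they are not. On that reading nearly all the unreachable cases disappear. This is fair, and the counts for truncation last are conditional. But the stated order (imputation, LOCF, then truncation) points the other way, and the text does not settle it.

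Third, the size should not be overstated. Truncation limits the values, not the shift itself: an eye imputed low can move well over 150 microns upward. After a significant result with 7 eyes imputed, the nullifying point is still reachable in 81–94% of simulated trials even with truncation last. After a null result with 7 missing, usually one point is lost but not always both: in a further simulation without covariates at least one was unreachable in 113/113 trials, and both in 56/113. All of this stands.

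Finally, SAP 8.6 says sensitivity analyses do not replace the primary analysis, and the trial is a pilot. That limits the consequence to how robustness is reported.

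**Conclusion.** The concern holds. The conclusion rule is wrong as written, and this needs no simulation: the quantity computed cannot bear on whether MAR is true. With MAR holding throughout, its median rose nearly threefold, from 80–90 to 230–240 microns, as imputed PBM eyes fell from 10 to 3.

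The order of shift and truncation is unspecified, and it matters most after a null result at the planned loss: at least one promised tipping point was missing in all simulated trials with truncation last, and in none with the shift applied afterwards. With 3 eyes missing per arm, at least one was missing under either order, so a reporting rule is needed whichever is chosen.

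The figures assume 67 per arm, residual SD 50, equal numbers missing in each arm and an imputation model without the interim visits that the SAP includes, so they are approximate. The primary test and the sample size are unaffected. This should be corrected before analysis, but it does not threaten the trial's main result.

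**What to change.** Make three changes to the tipping-point text in SAP 2.1:

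1. Replace the conclusion about MAR and the 500-micron example with a statement that the primary conclusion is robust to departures from MAR of up to X microns in imputed PBM eyes, reported with the number of imputed eyes in each arm.
2. State that the shift is applied after truncation or, equivalently for this purpose, that shifted values are not truncated.
3. State that, where no tipping point exists, the report says not reached and gives the largest shift tried with the treatment effect and P value attained there.

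The cost is a few sentences and one programming step. The primary analysis and data collection do not change.
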